**Please save frequently**

c) Describe the study design (e.g., single/double blind, parallel, crossover, control, experimental, observational, etc.). If the study is investigator-initiated, a timeline for individual subject recruitment, follow-up, and analysis for the study is required. Also, indicate if the subjects will be randomized.

This biomechanical study will use a repeated measures design to evaluate the effects of unilateral knee pain on contralateral knee joint loading during different types of walking. Thirty adults with unilateral symptomatic knee osteoarthritis will complete four, 1.5-hour study visits. The first and third visits will include level, inclined, and declined walking at comfortable, fast, and slow speeds. The second and fourth visits will include a 30-minute walk. There will be at least two days between visits. The only difference between each pair of visits is that one visit will involve walking with unilateral knee pain (painful walking) and the other visit will involve walking without unilateral knee pain (nonpainful walking). Individuals will be recruited based on the presence of unilateral knee pain so the painful walking will be representative of their typical walking. For the visits with nonpainful walking, the third and fourth visits, pain will be alleviated by performing an intraarticular injection with a local anesthetic (lidocaine). All walking will be performed in a three-dimensional motion capture environment on a split-belt treadmill that is instrumented with force plates.

A cohort of 30 healthy controls will complete the different walking conditions at two, 1.5-hour study visits. The healthy control group will not receive intraarticular knee injections. The purpose of this cohort is to better understand how walking mechanics in individuals with unilateral knee osteoarthritis compare to similar individuals without knee osteoarthritis.

d) If subjects will be given placebo, please justify placebo use. \*?HELP?\*

N/A

### 3. Study Procedures

a) N Is this project a multicenter study (i.e., same project is conducted elsewhere by a different investigator) OR does this study involve conduct of research at multiple sites? Is SLU acting as a coordinating center for other sites OR is the SLU PI a direct recipient of a federal grant for this research? If yes, complete and attach the Supplemental Application for Coordinating Center Activities.

Will the SLU site be participating in all parts/procedures/arms of the study?

If No, explain what SLU will NOT participate in:

**Please save frequently**

Page numbers from a sponsor's protocol/grant may be referenced in 3b, 3c, and 3d.

b) Describe all the procedures, from screening through end-of-study, that the human subject must undergo in the research project, including study visits, drug treatments, randomization and the procedures that are part of standard of care. Specify which procedures are for research and which are standard of care. Please note: The box below is for text only. If you would like to add

Protocol Title: Effect of knee pain on walking biomechanics

which are standard of care. Please note: The box below is for text only. If you would like to add tables, charts, etc., attach those files in the Attachment section (#16).

Potential participants will fill out a screening form in the REDCap Database designated for screening. This database will be monitored by the research team. If an individual is eligible, a member of the research team will call or email (based on preference reported on screening form) to schedule the participant for their first visit. If ineligible, a member of the research team will call or email the potential participant to notify them that they do not qualify for the study. If follow-up information is needed to determine eligibility, a member of the research team will call the potential participant to discuss and clarify any responses on the screening form.

Overview for those with knee osteoarthritis: Participants will be asked to complete four 1.5-hour visits where they fill out questionnaires and surveys, complete a clinical examination, and walk on a treadmill for approximately 30 minutes. At the third and fourth visits, participants will receive a knee injection prior to walking on the treadmill.

Overview for healthy participants: Participants will be asked to complete two 1.5-hour visits where they fill out questionnaires and surveys, complete a clinical examination, and walk on a treadmill for approximately 30 minutes.

Questionnaires and surveys: Demographics (age, sex, gender, race, ethnicity, and occupation) as well as a general and knee-specific medical history will be collected at the first visit. Medical history will include questions about past orthopedic injuries and any other medical conditions. Knee-specific medical history will include surveys and questionnaires about knee pain, function, quality of life, and treatments. In addition to these, participants will also complete questionnaires about their physical activity and comfort with treadmill walking at the first visit. The only questionnaires that will be repeated at the other three visits are the ones for assessing knee pain.

Specific questionnaires included in this study are 1) the Physical Activity and Sedentary Behavior Questionnaire (PASB-Q), 2) the Visual Analog Scale (for pain and treadmill comfort), 3) the Knee Injury and Osteoarthritis Outcome Score (KOOS) 4) PROMIS Scale – Pain Intensity 5) PROMIS Scale – Pain Interference 6) Intermittent and Constant Pain Score (ICOAP) questionnaire. Demographics and medical history questions are not a part of any particular questionnaire or survey.

Clinical examination: At each visit, participants will be asked to complete a clinical examination.

- Height and body mass will be measured with a stadiometer and digital scale, respectively.
- Blood pressure will be measured with a blood pressure cuff and stethoscope with participant in seated position.
- Pain sensitivity will be assessed with mechanical algometry at the knee and wrist. This will involve a researcher slowly applying pressure to the kneecap as well as the wrist with a device that has a rubber tip on the end. Once pain is perceived, participants will report it and the researcher will stop applying pressure. Throughout this assessment participants will be sitting with their knees bent to 90 degrees and feet flat on the floor. When assessing the wrist, participants will have their arm resting on a treatment table.
- Anatomic structures will be examined with ultrasound imaging. First, ultrasound gel will be applied to obtain an image. Researchers will then examine structures around your knee joint as well as structures that play a role in how the knee joint functions (e.g., calf, quadriceps, and hamstrings musculotendinous structures).

#### Walking Evaluation:

Speed determination and treadmill familiarization. At the first visit, participants will walk on a treadmill prior to performing the experimental walking conditions. The purposes of this walk are to determine a comfortable speed for level, inclined, and declined walking, and to familiarize the participant to walking on a treadmill. The speed of the treadmill will be set to 0.8 m/s at the beginning of the walk and modified based on feedback until a comfortable speed is determined. Familiarization will be completed when the participant feels comfortable and shows no outward

Protocol Title: Effect of knee pain on walking biomechanics

signs of being uncomfortable.

Setup. For each walking evaluation, 59 motion capture markers (small plastic balls) will be attached to the participant's pelvis, legs, and feet. At the first visit, markers will be placed after the familiarization walk to provide a 10- to 15-minute break from walking. For the other three visits, markers will be placed at the beginning of the visit since walking speed and familiarization will carry over from the first visit.

Once all markers are attached, participants will be asked to stand as still as possible for up to 30 seconds and perform dynamic hip trials. For dynamic hip trials, participants will be asked to flex, extend, abduct, and circumduct their hip to approximately 20 degrees. After both of these tasks are quality checked with the motion capture system, 26 markers will be removed, leaving 33 markers for tracking motion during the walking.

Intra-articular knee injections. Once the 26 markers are removed, participants will either begin the walking on the treadmill (visits 1 and 2) or receive an intraarticular knee injection and then proceed to walking on the treadmill (visits 3 and 4). If the participant is in the healthy control group, they will never receive a knee injection. If the participant is in the OA group, they will receive a knee injection at their third and fourth visits.

For the injections, 10 mL of 1% lidocaine hydrochloride will be put into the arthritic knee using a lateral approach. All injections will be sterile and ultrasound-guided to ensure safety and proper placement of drug within the knee joint. Within 5 minutes of the injection, the participant will experience numbness and likely significant decreases in pain. [name] and [name], licensed physicians in the School of Medicine at Saint Louis University, will perform all knee injections and monitor the participant for 15 minutes after the injections.

Walking analysis for those with knee osteoarthritis. At the first and third visits, participants will be asked to complete level, inclined, and declined walking at comfortable, fast, and slow speeds in a randomized order. The only difference between the first and third visits is that an injection of lidocaine hydrochloride will be received during the third visit before walking. Each type of walking will be performed for two minutes then immediately followed by two minutes of rest. For the inclined and declined walking, the treadmill will be set to 8.3% grade (4.8 degrees). This is the maximum gradient for public and business ramps set by the Americans with Disabilities Act, and is therefore representative of gradients that individuals with knee osteoarthritis are exposed to regularly. For the fast and slow walking at each of the gradients, the speed will be increased or decreased 20% of the comfortable walking speed determined during the familiarization walk.

In addition to the first and third visits, which involve nine types of walking, participants will walk for 30-minutes continuously at their second and fourth visits. The only difference between the two 30-minute walks is that an injection of lidocaine hydrochloride will be received during the fourth visit before walking. For these walks, participants will walk at their comfortable speed and 0% grade.

During the 30-minute walks individuals will have a functional near-infrared spectroscopy (fNIRS) cap placed on their head to monitor hemodynamic response in the cortex of the brain. fNIRS utilizes light-emitting diodes and receptors to measure blood oxygenation in the cerebral cortex (the outer portion of the brain). This is similar to how a pulse oximeter measures blood oxygenation in a finger. The overall safety of fNIRS is well established as minimal risk with a similar risk profile to conventional electroencephalography (EEG).

Pain with walking. For those with knee osteoarthritis, they will be asked to report the severity of their knee pain on a 0-to-10 scale after each type of walking and for every 5 minutes of walking during the 30 minute walks.

Walking analysis for healthy participants. Participants will complete the same types of walking that the participants with knee osteoarthritis complete. In other words, at the first visit

Protocol Title: Effect of knee pain on walking biomechanics

participants will be asked to complete level, inclined, and declined walking at comfortable, fast, and slow speeds, and at the second visit participants will be asked to walk for 30 consecutive minutes. During the 30 minute walk fNIRS will be used as described for the knee OA cohort.

Perceived exertion with walking. All participants will be asked to report their perceived level of exertion after each type of walking and for every 5 minutes of walking during the 30 minute walk.

c) If the proposed study is a clinical trial where a drug, vaccine, device or other treatment is compared to a placebo group or comparison treatment group, what are the guidelines or endpoints by which early decisions regarding efficacy or lack of efficacy can be made? For example, it may be reasonable to stop enrollment on a study when efficacy has already been clearly demonstrated, to avoid unnecessary enrollments of additional subjects. Alternatively, it may be reasonable to stop enrollment when it is clear that efficacy will never be demonstrated, given the statistical power of the study as designed. Describe the guidelines that are in place to assist in making these determinations, if relevant to the proposed study.

N/A

d) Describe how data analysis will be performed (statistical tests, methods of evaluating data) and indicate the smallest group/unit for which separate reporting will occur. For studies involving a questionnaire, if data and reliability information are available, please describe or provide references. For full board, unfunded studies describe sample size determination and power analysis. If none, please justify.

We will use descriptive statistics (e.g., means, medians, standard deviations, interquartile ranges) to describe each measurement, including those related to demographics, pain, structure, and biomechanics (movement and loading). Hypothesis testing will be completed using between and within group comparisons. Effect sizes, 95% confidence intervals, and metrics of significance will be calculated and used for interpretation. The smallest unit that will be reported are group level measures.

Please save frequently

e) State if deception (including incomplete disclosure of study purpose/procedures) will be used. If so, describe the nature of the deception and provide a rationale for its use. Also, describe debriefing procedures or justify a waiver of the requirement to debrief. NOTE: for studies using deception, an alteration of consent must be justified in the Informed Consent section of the protocol (#13) and the debriefing script/statement must be uploaded in the Attachments section (#16). See IRB Deception Guidelines.

f) Is there an accepted standard of care and/or standard practice at SLU for the condition/disease/situation being studied? This information will assist in comparing the risk/benefit ratio of study procedures relevant to usual care that would be received outside of the research context. \*?HELP?\* Y

If yes, please describe the standard of care and standard practice at SLU for the condition/disease/situation being studied.

There are numerous treatments for knee osteoarthritis, but none of them are considered the standard of care. Usual care for knee osteoarthritis depends on the healthcare team as well as the stage of disease. In early phases of disease, typical treatments include aerobic exercise,

Protocol Title: Effect of knee pain on walking biomechanics

strengthening, stretching, modalities (e.g., laser therapy, heat/ice, ultrasound, electrical stimulation, vibration), weight loss programs, walking programs, acupuncture, bracing and orthotics, and over-the-counter medications and supplements. In middle phases of disease, these treatments are typically supplemented with prescription medications and injectable therapies (e.g., platelet rich plasma, hyaluronic acid, corticosteroids). In late phases of disease, surgical procedures are strongly considered, such as joint realignment or replacement surgeries.

g) Does this study involve any diagnostic imaging, labwork or genetic testing that could result in clinical discovery (diagnoses, genetic mutations, etc.)? Note that this could include discovery that is expected (related to the research) or incidental (not related to research aims, but possible, like a mass/shadow found in imaging despite not looking for it).

If yes, please describe and include whether there are plans to share findings with study participants.

This study involves ultrasound imaging of the knee and anatomic structures around the knee. We expect to see structural changes that are common in individuals with knee osteoarthritis (e.g., joint space narrowing, calcifications, meniscal extrusion), but there is also a possibility for incidental findings. Both expected and incidental findings will be shared with participants. If the sonographer is concerned about any findings on imaging, the research team will ask the participant to reach out to their doctor for further examination and provide the participant with the images on a USB flash drive.

h) Is this study subject to the NIH Genomic Data Sharing Policy? N

The NIH GDS policy applies to all NIH-funded research that generates large-scale human genomic data as well as the use of these data for subsequent research and includes: genome-wide association studies (GWAS), single nucleotide polymorphisms (SNP) arrays, and genome sequence, transcriptomic, metagenomics, epigenomic and gene expression data, irrespective of NIH funding mechanism. Click here for more specific examples.

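### In the knee OA cohort the injected visit always comes second in each visit pair, so the painful versus nonpainful contrasts are confounded with visit order, although three sentences claim a single difference

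*Combined protocol and SAP*

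**What the plan says.** The protocol states the order openly. Section 2c: "For the visits with nonpainful walking, the third and fourth visits, pain will be alleviated by performing an intraarticular injection". Section 3b, in the part on injections, says: "Once the 26 markers are removed, participants will either begin the walking on the treadmill (visits 1 and 2) or receive an intraarticular knee injection". Visits 1 and 3 hold the nine short walking conditions; visits 2 and 4 hold the 30-minute walk. The only randomisation described is the order of the nine conditions within a visit.

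Three sentences then claim that one thing separates the paired visits:

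- Section 2c, both pairs: "The only difference between each pair of visits is that one visit will involve walking with unilateral knee pain (painful walking", with the other visit being nonpainful.
- Section 3b, visits 1 and 3: "The only difference between the first and third visits is that an injection of lidocaine hydrochloride will be received during the third visit before walking".
- Section 3b, visits 2 and 4: "The only difference between the two 30-minute walks is that an injection of lidocaine hydrochloride will be received during the fourth visit before walking".

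Other parts of Section 3b describe steps that belong to visit 1 alone. The speed-setting and familiarization walk takes place there. On questionnaires: "The only questionnaires that will be repeated at the other three visits are the ones for assessing knee pain". On setup: "At the first visit, markers will be placed after the familiarization walk to provide a 10- to 15-minute break from walking", whereas at the later visits "markers will be placed at the beginning of the visit since walking speed and familiarization will carry over from the first visit".

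Section 3d (data analysis) announces between-group and within-group comparisons with effect sizes and 95% confidence intervals. It mentions no visit or order effect.

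**The concern.** Hypotheses 1.1, 2.1 and 2.2 in Section 2b compare painful with nonpainful walking. In the OA cohort that comparison is also earlier session against later session. Anything that changes between sessions, such as treadmill experience, adaptation to the laboratory or symptom fluctuation, is counted in the difference and could enlarge it or hide it. A reader who accepts the three sentences would take the result as the effect of pain alone, which the design cannot deliver. The healthy cohort does not help, because it has two visits and nothing that corresponds to visits 3 and 4.

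**Working it through.** **No stated figure to reproduce.** The documents give no power, effect size or SD. The counts agree: 3 gradients × 3 speeds = 9 conditions, and 30 + 30 = 60 participants.

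**Aliasing.** Code the OA schedule from Sections 2c and 3b:

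| Visit | Injected | Format |
|---|---|---|
| 1 | 0 | nine 2-minute bouts |
| 2 | 0 | 30-minute walk, fNIRS cap |
| 3 | 1 | nine 2-minute bouts |
| 4 | 1 | 30-minute walk, fNIRS cap |

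For visits 1 and 3 the matrix [1, injected, visit] has rows (1, 0, 1) and (1, 1, 3), hence rank 2 of 3. Visits 2 and 4 give the same. The expected paired difference is π + s, where π is the effect of pain relief and s the session effect; only the sum is estimable. Randomising the nine conditions within a visit does not alter these rows. With visit as a four-level factor over all four visits, the rank is 4 of 5, so pain is still aliased.

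**Visits 1 and 3 against the single-difference claim.** Three things occur at visit 1 only: the speed-setting and familiarization walk, marker placement after that walk, and the full set of questionnaires. The claim is contradicted on the page.

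**Visits 2 and 4.** The setup is the same, so there is no such contradiction. What the sentence leaves out is history. Experimental walking completed before visit 2 is 9 × 2 = 18 minutes. Before visit 4 it is 18 + 30 + 18 = 66 minutes, together with one earlier injection.

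**Which hypotheses are exposed.** H1.1, H2.1 and H2.2 carry s in full. H1.2 compares pain effects across gradients: (π_incline + s) − (π_level + s) = π_incline − π_level. A shift common to all gradients cancels; only a gradient-specific one remains.

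**Illustration of size.** Assumptions, none from the documents: 30 complete pairs, two-sided 5% paired t-test, shifts in SD of the paired difference. The rejection probability comes from the noncentral t with 29 df and noncentrality δ√30.

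| Session shift, no true effect | Declared significant |
|---|---|
| 0 | 5.0% |
| 0.1 | 8.3% |
| 0.2 | 18.5% |
| 0.3 | 35.5% |
| 0.5 | 75.4% |

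In the other direction, a true effect of 0.53 SD has 80.1% power. Opposing shifts of 0.2, 0.3 and 0.5 leave net effects of 0.33, 0.23 and 0.03, with power 41.6%, 23.0% and 5.3%.

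**Can the planned data separate drift from pain?** Level walking at comfortable speed occurs at all four visits, which suggests comparing visit 1 with visit 2 and visit 3 with visit 4. But format alternates with visit. With format coded 0, 1, 0, 1, visit = 1 + 2 × injected + format exactly, so [1, injected, visit, format] has rank 3 of 4. Healthy controls have the same two formats, and adding them with a group term gives rank 4 of 5. Those comparisons therefore measure drift plus format. A linear-drift adjustment uses weights 0.5, −1.5, 1.5, −0.5 on visits 1 to 4. A format effect B, which cancels in 1 vs 3 and in 2 vs 4, would enter the adjusted pain effect as −1.5B − 0.5B = −2B.

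**The case against.** The best defence is that nothing is concealed. The order is given in the same paragraph as the Section 2c sentence, both 3b sentences name the injected visit, and the visit-1 steps are described shortly before. Session effects are also restrained: familiarization continues until the participant is comfortable, the speed is carried forward, condition order is randomised, and visits are at least two days apart. The sentence on visits 2 and 4 can be read as describing the two walks, whose setup is the same.

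Much of this stands. The order is disclosed, the precautions are sensible, and the 2 versus 4 sentence is incomplete rather than contradicted. But disclosure of the order does not make a single-difference claim true, and the precautions may shrink s without making it separable from π.

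Two further points are fair. Section 3d is a short summary in an ethics application. The grant proposals to which Section 1a refers are not among these documents, so it cannot be said that no order analysis exists anywhere. They could not, however, make the three sentences accurate. In addition, the Section 3 and Section 8k text describes a study that may be well advanced: Section 8k plans analyses to January 2024. That does not matter for a correction of wording and interpretation.

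A reader might infer that the study's results are biased by drift. The documents do not support that: they report no session effect, and the rejection rates above show only what would follow from assumed shifts. A reader might also infer that the four visits of level walking allow the confounding to be tested or adjusted away. The format argument shows that they do not.

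**Conclusion.** The point holds as a matter of design and wording, and should be fixed. In the OA cohort, 1 vs 3 and 2 vs 4 each estimate the difference before versus after lidocaine plus any effect of visit order. The aliasing is complete and rests on the stated schedule alone, with no distributional assumption. The single-difference claim is contradicted for 1 vs 3 and incomplete for 2 vs 4. H1.1, H2.1 and H2.2 are affected; H1.2 only if the session effect differs by gradient.

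The practical size is unknown. The illustrative figures depend on the assumed test, 30 complete pairs and assumed shifts, and are not evidence of bias. It would go too far to conclude that the fixed order makes the study uninformative or that the schedule must change. The contrasts remain interpretable as before-versus-after differences.

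**What to change.** Leave the visit and injection schedule as it is.

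1. Correct the sentence in Section 2c and the two in Section 3b. They should say that the uninjected visit always precedes the injected one. For visits 1 and 3 they should add that the speed-setting and familiarization walk, marker placement after it and the full questionnaires occur at visit 1 only. For visits 2 and 4 they should say that the setup is the same but that visit 4 follows more walking and an earlier injection.
2. Add to Section 3d, in words such as: *In the OA cohort the contrasts of visit 1 with visit 3 and of visit 2 with visit 4 estimate the difference before versus after lidocaine. They are confounded with visit order and will not be reported as the effect of pain alone.* Carry the same statement into the reports of H1.1, H2.1 and H2.2. For H1.2, state the assumption that any session effect is equal across gradients.

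I do not recommend a drift test or a drift-adjusted pain effect from level walking, because of the format confounding shown above. Nor do I recommend adding an uninjected walk at visits 3 and 4: it would add a procedure and split the cohort between two protocols.

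The cost is a text amendment and a weaker causal statement. No visit time, participants or measurements are added.
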